3. INTERIM ANALYSIS AND DATA MONITORING COMMITTEE REVIEW

3.1. Interim Analysis

Before the first DBL at Week 16, an interim analysis will be conducted when a subset of the participants who received at least one administration of study agent (including a partial dose) have completed their Week 16 visit or have terminated their study participation before Week 16. Details of the plan for the interim analysis will be specified in a separate IAC charter and interim analysis plan document before the interim analysis is performed. The interim analysis will be used to determine whether the efficacy of guselkumab 1200 mg IV and guselkumab 200 mg SC doses, as measured by the primary endpoint, is sufficiently low to consider terminating the study based on prespecified guidelines from the data accrued up to the interim analysis. Interim analysis results will not be disseminated to investigators or individuals involved with the conduct of the study.

An interim analysis committee otherwise not involved in the study conduct will be responsible for reviewing the results of this interim analysis. Detail of the organization and roles and responsibilities of the committee, interim analysis procedure, analysis methods, possible recommendations or requests, and the communication following this review will be specified in interim analysis committee charter and analysis plan document.

3.2. Data Monitoring Committee

An independent, external DMC has been established to monitor data on an ongoing basis to ensure the continuing safety of the participants enrolled in this study. The DMC consists of 3 members who are independent of the sponsor. None of the members is participating as an investigator in the current study.

The major function of the DMC is to monitor the safety of the study agent by reviewing the serious adverse events (SAEs) each month and by reviewing the study safety data approximately every 3/4 months. The content of the safety summaries for this study are defined and documented in the DMC SAP developed by the sponsor. No hypothesis testing will be conducted. An independent statistical supporting group, provided by COVANCE (Chiltern), supports the DMC and is the liaison between sponsor and the DMC.

After each review, the DMC is to make recommendations regarding the continuation of the study as planned or, in the event that any unanticipated concerning safety events or issues occur, placing the study on hold or stopping the study. In addition, the DMC roles and responsibilities, and the general procedures (including communications) are defined and documented in the Data Monitoring Committee charter developed by the sponsor detailing the safety data monitoring to be conducted by the DMC.

4. SUBJECT INFORMATION

Unless specified otherwise, FAS will be used for the subject information analyses and participants will be analyzed according to the treatment group to which they were randomized at Week 0, regardless of the treatment they actually received. The number of participants in FAS will be summarized by treatment group and overall.

Simple descriptive statistics, such as mean, median, standard deviation, interquartile range, maximum, and minimum for continuous variables, and counts and percentages for discrete variables will be used to summarize most data and no formal hypothesis testing for treatment comparisons will be performed. In addition, subject listings will also be used to present the data.

4.1. Demographics and Baseline Characteristics

The full analysis set will be used for all tabulations. Participants' demographic data and baseline disease characteristics will be summarized by treatment group. In addition, summaries of participants' medical history and current diagnoses, alcohol intake, and smoking status will be provided by treatment group. If imbalances are found at baseline, then additional analyses may be performed adjusting for baseline differences.

4.1.1. Demographic

[Table 2](#) presents a list of the demographic variables that will be summarized by treatment group, and overall for the FAS.

Table 2: Demographic Variables

Continuous Variables:	Summary Type
Age (years)	Descriptive statistics (N, mean, standard deviation [SD], median and range [minimum and maximum], and IQ range).
Weight (kg)	
Height (cm)	
Categorical Variables:	
Age (<40 years, 40 to <65 years, and ≥65 years)	Frequency distribution with the number and percentage of participants in each category.
Sex (male, female)	
Weight (kg) (≤ 95 kg, > 95 kg)	
Race (American Indian or Alaska Native, Asian, Black or African American, Native Hawaiian or other Pacific Islander, White, Multiple)	
Ethnicity (Hispanic or Latino, Not Hispanic or Latino)	
BMI (Normal [<25], Overweight [25 -<30], Obese [≥30])	

4.1.2. Baseline Disease Characteristics and Medical History

Baseline disease characteristics (e.g., duration of HS disease, baseline Hurley stage status, baseline AN count, inflammatory nodule count, abscess count, and draining fistula, HS-IGA, and PRO related measurements) will be summarized by treatment group. In addition, summaries of participants' medical history and current diagnoses, alcohol intake, and smoking status will be provided by treatment group and the distribution of participants by Hurley stage status (I, II, and III) and weight category (≤95 kg, >95 kg) will also be provided.

4.2. Disposition Information

Disposition data will be summarized through the study periods that include the following:

- Through Week 16
- Through Week 48

The number of participants in the following disposition categories will be summarized by treatment group and overall:

- Participants randomized
- Participants who received study agent
- Participants who discontinued study agent
- Reasons for discontinuation of study agent

- Participants who completed the study
- Participants who terminated study prematurely
- Reasons for termination of study

Listings of participants will be provided for the following categories:

- Participants who discontinued study agent
- Participants who terminated study prematurely
- Participants who were unblinded during the study period
- Participants who were randomized yet did not receive study agent
- In addition, screened participants will be summarized overall.

4.3. Treatment Compliance

Study agent compliance will be summarized descriptively through Week 36 for the FAS. Number of participants by randomized treatment versus actual treatment will be presented in a summary table. Number of the participants receiving each scheduled treatment will be summarized. In addition, treatment compliance will also be assessed by protocol deviations related to study agent administration (i.e., incorrect study agent or dose received).

4.4. Extent of Exposure

The exposure data through Week 16 and through Week 36 will be summarized. The number and percentage of participants who receive study agent will be summarized by treatment group for the safety analysis set. Descriptive statistics will be presented for the following parameters:

- Number of administrations
- Cumulative total dose

Study agent lots received by treatment, including matching placebo for active treatment will be summarized.

In addition, the average exposure (number of administrations) and average duration of follow-up (weeks) will also be summarized by treatment group in the safety tables through different study time periods.

4.5. Protocol Deviations

In general, the following list of major protocol deviations may have the potential to impact participants' rights, safety or well-being, or the integrity and/or result of the clinical trial. Participants with major protocol deviations will be identified prior to database lock and will be summarized by category by treatment group through Week 48 for the FAS.

- Entered but did not satisfy criteria
- Developed withdrawal criteria but not withdrawn

- Received a disallowed concomitant treatment
- Received wrong treatment or incorrect dose
- Other: to be defined in the major protocol deviation criteria document

In addition, a listing of participants with major protocol deviations and a listing of participants who missed scheduled study agent administrations (including SC injections and/or IV infusions) will also be provided by randomized treatment group.

4.6. Prior and Concomitant Medications/Surgeries

Prior and concomitant medications will be summarized by treatment group. Prior medications are defined as any therapy used before the day of first dose (partial or complete) of study agent. Concomitant medications are defined as any therapy used on or after the same day as the first dose of study agent, including those that started before and continue on after the first dose of study agent.

Prior HS treatment received (including prior HS related surgery) and the reasons for which participants discontinued these treatments will be summarized by randomized treatment group for the FAS. In addition, a summary of concomitant analgesic therapy for HS, a list of participants who received a protocol-prohibited concomitant treatment meeting the definition of a treatment failure and a listing of participants who received concomitant analgesic therapy meeting the definition of a treatment failure of pain related endpoints will also be provided.

Participants who received concomitant systemic corticosteroids for indications other than HS and participants with concomitant prophylactic treatments for latent TB infection will be listed.

5. EFFICACY

5.1. General Method of Analysis

Unless specified otherwise, efficacy data summaries will be provided by treatment group for the FAS. Statistical comparisons will be made between each of the guselkumab treatment groups (1200 mg IV, 200 mg SC q4w) and the placebo treatment group.

In general, for response efficacy endpoints, treatment comparisons will be performed using a Cochran-Mantel-Haenszel (CMH) test stratified by the baseline weight (≤ 95 kg, >95 kg) and baseline Hurley stage (I, II, and III). For continuous efficacy endpoints, treatment comparisons will be performed using either a Mixed-Effect Model Repeated Measure (MMRM) model or an analysis of covariance (ANCOVA) model. All of the models will have treatment group, baseline weight (≤ 95 kg, >95 kg), baseline Hurley stage (I, II, and III), and baseline value as explanatory factors. The MMRM model will also include visit, treatment group by visit interaction, and baseline value by visit interaction as additional explanatory factors. In addition, treatment differences and their associated 95% confidence intervals will be presented.

If the total number of participants that are Hurley stage I at baseline is less than 18, participants that are Hurley stage I will be pooled with the participants that are Hurley stage II, when analyses are adjusted by Hurley stage. Descriptive statistics, such as mean, median, standard

deviation, minimum and maximum, interquartile range for continuous variables, and counts and percentages for categorical variables will be used to summarize the data. Graphical data displays and subject listings may also be used to summarize the data.

5.2. Analysis Specifications

5.2.1. Level of Significance

[figure not shown]
Unless otherwise specified, all statistical testing procedures will be performed at a 2-sided significance level of 0.05. This study is designed to maintain an overall Type I error of 0.1 or less for the primary analysis and major secondary analyses. Nominal p-values will be reported for other secondary analyses.

5.2.1.1. Multiplicity Adjustment for Testing Procedures

This study has 1 primary endpoint (proportion of participants who achieved Hidradenitis Suppurativa Clinical Response (HiSCR) at Week 16) and 3 major secondary endpoints. With 2 treatment comparisons for each of these endpoints, there are a total of 8 hypotheses to be tested.

The primary and major secondary hypotheses will be tested in the specified order and the order and procedure are shown in [Figure 2](#).

Figure 2: Diagram for Multiple Testing Procedure for Primary and Secondary Hypotheses

With the sequential analyses specified above within each dose group vs placebo, each of the hypotheses will be tested at a 2-sided α -level of 0.05 provided that the significance is achieved for the preceding hypothesis test in the specified order shown in [Figure 2](#). If a given comparison is not significant at the 2-sided α -level of 0.05, nominal p values will be provided for the subsequent treatment group comparisons within each dose group vs placebo and these comparisons will be considered as supportive.

5.2.2. Definition of the Efficacy Endpoints and Calculation of the Efficacy Instruments

5.2.2.1. Hidradenitis Suppurativa Clinical Response (HiSCR)

HiSCR responder status is defined as at least a 50% reduction from baseline in the total abscess and inflammatory nodule count, with no increase in abscess or draining fistula count.

5.2.2.2. Lesion Counts

Lesion counts are defined as the number of abscesses, inflammatory nodules, non-inflammatory nodules, draining fistulas, and non-draining fistulas. Lesions will be counted during each visit.

AN Count

- AN count is defined as total abscess and inflammatory nodule count.
- AN50 is defined as at least a 50% reduction in AN count relative to baseline.
- AN75 is defined as at least a 75% reduction in AN count relative to baseline.
- AN90 is defined as at least a 90% reduction in AN count relative to baseline.
- AN100 is defined as a 100% reduction in AN count relative to baseline (ie, AN count = 0).

5.2.2.3. Hurley Staging

Hurley staging consists of 3 stages of disease:

- Stage I: Abscess formation, single or multiple, without sinus tracts and scarring
- Stage II: One or more widely separated recurrent abscesses with tract formation and scarring
- Stage III: Multiple interconnected tracts and abscesses across the entire area, with diffuse or near diffuse involvement

5.2.2.4. Hidradenitis Suppurativa Investigator's Global Assessment

The HS-IGA documents the investigator's assessment of the participant's HS at a given timepoint. The anatomic region with the most severe HS activity at baseline visit should be evaluated for erythema, drainage, and pain and/or tenderness to palpation for each participant. For each participant, the same anatomic site selected for evaluation at baseline visit should then be evaluated at each subsequent visit.

The participant's HS-IGA is assessed as inactive (0), almost inactive (1), mild activity (2), moderate activity (3), or severe activity (4). A higher score indicates more severe disease.

The participant's HS-IGA of erythema is assessed as no erythema, hypopigmentation or hyperpigmentation may be present (0), faint, barely perceptible erythema (1), light red color (2), moderate red color (3), or bright red coloration (4). A higher score indicates more severe disease.

The participant's HS-IGA of drainage is assessed as no drainage, areas are dry following palpation (0), slight pain and/or tenderness with palpation (1), mild pain and/or tenderness with palpation (2), moderate amount of spontaneous drainage (3), or severe spontaneous drainage occurring over broad area(s) (4). A higher score indicates more severe disease.

The participant's HS-IGA of pain and/or tenderness to palpation is assessed as no pain and/or tenderness with palpation (0), slight pain and/or tenderness with palpation (1), mild pain and/or tenderness with palpation (2), moderate pain and/or tenderness with palpation, participant winces (3), or severe pain and/or tenderness with palpation, participant winces and attempts to withdraw (4). A higher score indicates more severe disease.

5.2.2.5. Patients Reported Outcomes

5.2.2.5.1. Hidradenitis Suppurativa Symptom Diary

The HSSD (Section 10.11 of the protocol [Appendix 11]) is a 7-item patient self-reported questionnaire that assesses 5 HS-related symptoms including pain, tenderness, hot skin feeling, odor, and itchiness. The participants are asked to rate the severity of each symptom on a 0 to 10 numerical rating scale, with 0 indicating no symptom experience and 10 indicating the worst possible symptom experience. All 5 symptoms have a recall period of the past 7 days, except for 2 additional questions on pain which evaluate current pain and pain in the past 24 hours. Each individual symptom scale score, ranging from 0-10, will be summarized. A total symptom score, which will also range from 0-10, will be derived by averaging the 5 individual scale scores that utilize the past 7-day recall period.

5.2.2.5.2. Dermatology Life Quality Index

The DLQI is a dermatology-specific quality of life instrument designed to assess the impact of the disease on a subject's quality of life. It is a 10-item questionnaire that, in addition to evaluating overall quality of life, can be used to assess 6 different aspects that may affect quality of life: symptoms and feelings, daily activities, leisure, work or school performance, personal relationships, and treatment. The DLQI is calculated by summing the score of each question resulting in a maximum of 30 and a minimum of 0. A higher score indicates more severe disease. A score of ≤ 1 indicates no effect at all of disease on subject's health related quality of life, and a reduction of 5 points or more in total DLQI score is considered clinically meaningful improvement.

For a partially answered questionnaire (eg, not all 10 answers in the DLQI questionnaire were available):

- If one question's answer is not available, this question will be scored 0. The total score will then be calculated.
- If two or more questions' answers are unavailable, the questionnaire is not scored. Hence, the total score and each of the 6 component scores will be set to missing.
- If one question from one of the 6 component scores is missing, the affected component score will be set to be missing.

5.2.2.6. Hospital Anxiety and Depression

The Hospital Anxiety and Depression Scale (HADS), a self-assessment scale, was developed to detect states of depression, anxiety and emotional distress amongst patients who were being treated for a variety of clinical problems. The HADS consists of 2 subscales, one measuring Anxiety (A-scale) and one measuring Depression (D scale), which are scored separately.

The HADS is a 14-item questionnaire. Seven of the items relate to anxiety and seven relate to depression. Each item on the questionnaire is scored from 0-3 resulting in a score between 0 and 21 for either anxiety or depression.

If one or more of the items within each domain are left unanswered, that HADS component score will be considered missing.

5.2.3. Data Handling Rules

The following treatment failure rules and data handling rules will be applied to the efficacy analyses in this study.

5.2.3.1. Treatment Failure Criteria

Participants who discontinue study intervention due to lack of efficacy or an AE of worsening of HS, or who started a protocol-prohibited medication or therapy during the study that could improve HS, are considered treatment failures.

The particular protocol-prohibited medications/therapies include:

Systemic Therapies:

- Any immunodulatory biologic therapy
- Any conventional systemic immunosuppressive therapy
- Any systemic corticosteroid for HS
- Any systemic antibiotic therapy for HS or any indications other than infection
- Any systemic retinoid

- Investigational Agents for HS
- Analgesic therapy for HS (Section 5.2.3.2.1)
- Phototherapy (PUVA and/or UVB) for any indications and other phototherapies for indication of HS

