6.5.4. Analgesic Therapy

Use of opioid analgesics is prohibited for 14 days prior to the baseline visit regardless of HS or non-HS reasons. During the study, concomitant use of opioid analgesics is also prohibited, with the exception of tramadol as detailed below.

Oral analgesics for HS-related pain are prohibited 14 days prior to the baseline visit. If a participant is on a stable dose of a non-opioid analgesic (PRN is not considered stable) for a non-HS medical condition (eg, osteoarthritis), the participant may continue the analgesic, provided the dose is stable for 14 days prior to baseline and is anticipated to remain stable throughout study participation.

If a participant's pain (HS-related or non-HS-related) worsens after baseline, they may initiate analgesic therapy at any time as follows:

For HS-related pain, permitted analgesics are limited to:

- Ibuprofen (at a dose of up to 800 mg by mouth every 6 hours) not to exceed 3.2 grams/24 hours; AND/OR
- Acetaminophen as per local labeling; AND/OR
- If HS-related pain is uncontrolled with ibuprofen and/or acetaminophen at the above dosing regimens after the baseline visit, participants can be prescribed tramadol (at a dose of up to 100 mg by mouth every 4 hours), not to exceed 400 mg/24 hours.

Dose adjustments of ibuprofen, acetaminophen, or tramadol, and use of these analgesics on an "as needed" (PRN) basis for HS-related pain up to the maximum permitted dose and frequency, are allowed during the study.

From Screening through Week 40, participants will not be permitted to use any analgesics related to HS pain within 24 hours of a scheduled study visit. All analgesics and dose adjustments will be captured in the source and on the appropriate eCRF.

For non-HS-related pain:

• All other non-opioid analgesics and tramadol are allowed at the recommended or prescribed dose.

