5.2.3.2. Treatment Failure Rules

A participant who meets one or more of the treatment failure criteria specified in Section 5.2.3.1 will be considered a treatment failure from that point onward. The baseline values will be used for all directly measured endpoints regardless of the actual measurements. Zero will be assigned to improvement, and non-responder status will be assigned to binary response variables. However, treatment failure rules for the HSSD pain related endpoints will be handle differently and are specified in Section 5.2.3.2.1.

Treatment failure is assumed to have occurred at the earlier of the following dates:

- Date of discontinuation of study treatment due to lack of efficacy or an AE of worsening of HS or
- Date of initiation of a protocol-prohibited medication/therapy during the study that could improve HS.

In addition, lesions that received intervention as rescue therapy will be counted as present after the visit of intervention.

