5.3.3. Data Handling

The data handling rules specified in Section 5.2.3.3 and 5.2.3.3.1 will be applied to the primary analysis. In the case of participants with missing components (abscess, inflammatory nodule, or draining fistula counts) at Week 16, LOCF will be applied for the missing lesion count(s). This partial component missing data imputation rule will be applied to all the following analyses related to the primary endpoint.

Participants who meet treatment failure criteria specified in Section 5.2.3.2 prior to Week 16 will be considered not achieving HiSCR at Week 16. In addition, for participants who do not return for evaluation at Week 16 will be considered as non-responders.

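### Read literally, SAP 5.2.3.1 and 5.2.3.2 let HS analgesic use before Week 16 count as HiSCR failure, in conflict with Protocol 6.5.4 and with SAP 5.2.3.2.1 and 4.6

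*SAP*

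**What the plan says.** SAP 5.2.3.1 sets the general condition: besides those who stop treatment for lack of efficacy or worsening HS, participants "who started a protocol-prohibited medication or therapy during the study that could improve HS, are considered treatment failures". It then lists the prohibited therapies. One bullet is "Analgesic therapy for HS (Section 5.2.3.2.1", the only bullet in the list with a cross-reference.

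SAP 5.2.3.2 gives the consequence. Anyone "who meets one or more of the treatment failure criteria specified in Section 5.2.3.1 will be considered a treatment failure from that point onward". Directly measured endpoints take their baseline values, and "non-responder status will be assigned to binary response variables". The one exception reads: "treatment failure rules for the HSSD pain related endpoints will be handle differently and are specified in Section 5.2.3.2.1".

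SAP 5.2.3.2.1 has its own trigger (an HS analgesic within 1 day of a scheduled visit), its own scope (HSSD past-24-hour and current pain) and its own duration (that visit). It leaves the 7-day-recall pain item outside the failure rules altogether.

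SAP 5.3.3 carries the general criteria to the primary endpoint: participants who meet them "prior to Week 16 will be considered not achieving HiSCR at Week 16".

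Protocol 6.5.4 says that if pain worsens after baseline, participants "they may initiate analgesic therapy at any time as follows". It names ibuprofen, acetaminophen and, if these fail, tramadol for HS pain, all usable as needed. It forbids HS analgesics within 24 hours of a scheduled visit from Screening through Week 40.

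SAP 4.6 plans two separate outputs: one for prohibited treatment that meets the failure definition, and one for analgesic use that meets the failure definition for pain-related endpoints.

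**The concern.** The exception in SAP 5.2.3.2 is written by endpoint (HSSD pain), not by trigger (analgesic use). It changes how pain endpoints are handled. It does not say that an analgesic-triggered failure stops there. A programmer who works through 5.2.3.1, 5.2.3.2 and 5.3.3 in order can therefore set HiSCR to non-response for anyone recorded with HS analgesic use before Week 16. The same rule would set AN count and DLQI change to zero from that point on.

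The result would be lopsided. The 24-hour pain score, which an analgesic affects directly, would fail only at the affected visit. The lesion-based endpoints would fail permanently. The primary endpoint and two of the three major secondary endpoints are exposed.

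The planned checks would not show the problem. Both sensitivity analyses in SAP 5.3.4 and the per-protocol analysis in 5.3.6 keep the treatment-failure rules. HiSCR without those rules appears only in over-time summaries (SAP 5.5.4, and 5.5.2.2 for the Week 16 lock).

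**Working it through.** **Step 1. The text allows three readings.**

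| Reading | Trigger | Effect on HiSCR at Week 16 | Support |
|---|---|---|---|
| Broad | Any HS analgesic use after baseline | Non-responder | The bullet has no limit on agent or timing in its own words; 5.2.3.2 makes any 5.2.3.1 criterion permanent |
| Middle | Only use that Protocol 6.5.4 prohibits, chiefly within 24 hours of a visit | Non-responder | Such use is prohibited, it is on the SAP list, and the 5.2.3.2 exception covers only pain endpoints |
| Pain-only | HS analgesic within 1 day of a visit | None | Cross-reference to 5.2.3.2.1; separate outputs in 4.6 |

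The broad reading conflicts with Protocol 6.5.4, because it treats as prohibited what the protocol permits. The broad and middle readings both go beyond SAP 5.2.3.2.1 and 4.6. The pain-only reading fits the most passages, but no sentence states it for HiSCR, AN count or DLQI.

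**Step 2. Reproduce the design power.** The inputs from Protocol 9.2 are 60 per arm, placebo 25%, guselkumab 55%. SAP 1.4 gives two-sided alpha 0.05. The formula is the unstratified normal approximation with pooled variance under the null:

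power = Φ{ [Δ − 1.96·√(2p̄(1−p̄)/n)] / √[p₁(1−p₁)/n + p₂(1−p₂)/n] }

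With p̄ = 0.40:

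- √(2 × 0.40 × 0.60/60) = 0.0894, times 1.96 = 0.1753
- √[(0.1875 + 0.2475)/60] = 0.0851
- (0.30 − 0.1753)/0.0851 = 1.46, so power = 92.9%

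Table 1 states 93%. The other five rows reproduce within 1 point (84.1, 94.1, 98.4, 81.6 and 98.0 against 85, 94, 98, 82 and 98).

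**Step 3. Pain-only reading.** HiSCR status does not change, so power stays at 92.9%.

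**Step 4. Broad reading, equal use.** Let q be the fraction of participants with HS analgesic use before Week 16. The documents give no value, so q is assumed. If use is independent of response and equal in both arms, each rate is multiplied by (1 − q):

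| q | Placebo | Guselkumab | Difference | Power |
|---|---|---|---|---|
| 0% | 25.0% | 55.0% | 30.0 points | 92.9% |
| 10% | 22.5% | 49.5% | 27.0 points | 87.9% |
| 20% | 20.0% | 44.0% | 24.0 points | 81.3% |
| 30% | 17.5% | 38.5% | 21.0 points | 73.2% |
| 50% | 12.5% | 27.5% | 15.0 points | 53.8% |

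**Step 5. Broad reading, unequal use.** Use is still assumed independent of response within each arm:

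| Use, placebo / guselkumab | Placebo | Guselkumab | Difference | Power |
|---|---|---|---|---|
| 20% / 30% | 20.0% | 38.5% | 18.5 points | 60.8% |
| 30% / 20% | 17.5% | 44.0% | 26.5 points | 89.2% |
| 40% / 20% | 15.0% | 44.0% | 29.0 points | 94.6% |

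With no true effect (25% in both arms) and 40% / 20% use, the rule gives 25% × 0.6 = 15% against 25% × 0.8 = 20%. That is a spurious 5-point difference in favour of guselkumab.

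Under the middle reading q counts only users of prohibited analgesics, so it would be no larger than under the broad reading.

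**The case against.** A reader might infer that, under the SAP as it stands, one dose of permitted ibuprofen makes a participant a HiSCR non-responder. The documents do not support that as settled, for three reasons.

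- The bullet points to 5.2.3.2.1, which limits trigger, endpoint and visit. If the bullet were unrestricted, the cross-reference would do no work.
- The general condition in 5.2.3.1, repeated where 5.2.3.2 dates the failure, requires a therapy that is protocol-prohibited and could improve HS. Protocol 6.5.4 permits these analgesics away from visits, and the prohibited list in Protocol 6.5.5 names none. It is also hard to argue that an analgesic improves lesion counts.
- SAP 4.6 describes the analgesic failure as one of pain-related endpoints and lists it apart from the general failures.

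These points stand as evidence of intent. They do not close the gap. The protocol-prohibited condition protects little when the SAP's own list places HS analgesics under that label. Use within 24 hours of a visit is prohibited by Protocol 6.5.4, as are opioids other than tramadol, so the middle reading survives that condition.

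A reader might also take the power losses as expected. They are not. They hold only under the literal reading and assumed use rates. Protocol 6.5.4 ties starting an analgesic to worsening pain, so users may be mostly non-responders already, and reclassifying them would then change less than Step 4 shows.

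**Conclusion.** The point holds as a conflict in the rule that sets responder status on the primary endpoint. Read literally, SAP 5.2.3.1 and 5.2.3.2 turn HS analgesic use before Week 16 into HiSCR failure and reset AN count and DLQI. This applies at least to use within 24 hours of a visit and arguably to permitted use. SAP 5.2.3.2.1 and 4.6 indicate that only pain endpoints, at the affected visit, were meant.

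The size depends on the reading. Under the pain-only reading it is nil. Under the literal reading, with equal use independent of response, power would fall from 93% to about 88% at 10% use and about 73% at 30% use. With unequal use the difference could be biased either way. The use rates are assumptions, and the calculation approximates the planned stratified CMH test by an unstratified one. The documents do not show that any such loss will occur. They show that the analysis could be programmed in ways that give different primary results.

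**What to change.** Keep the bullet in SAP 5.2.3.1, so that the link to the pain rule is not lost, but restrict it: HSSD past-24-hour and current pain endpoints only, at the affected visit (Section 5.2.3.2.1). Add one sentence to 5.2.3.2 saying that HS analgesic use alone does not trigger treatment failure for HiSCR, lesion counts, DLQI, HS-IGA or HADS. Check that 4.6, 5.2.3.1, 5.2.3.2 and 5.2.3.2.1 then agree with each other and with Protocol 6.5.4.

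Make the change before the Week 16 database lock, when selected sponsor personnel are unblinded. The interim analysis also uses the primary endpoint, so its separate plan should apply the same wording. The cost is one phrase and one sentence in the SAP. No new data are needed, and no rule on which analgesics participants may use is altered.
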